7.4.2 Proteinuria

Patients will be monitored for proteinuria by dipstick every two weeks during Cycle 1 and Cycle 2 and every 28 days thereafter. Patients with early signs of proteinuria by dipstick (2+) should be closely monitored and proteinuria evaluated quantitatively (24 hours protein excretion or protein-to-creatinine ratio). Additional safety monitoring should be performed as clinically indicated including tests for the assessment of free/conjugated bilirubin, haptoglobin N, schizocytes, or renal biopsy.

The following treatment and lucitanib dose adjustments algorithm should be followed in case proteinuria is encountered:

Table 3: Proteinuria Management Algorithm

In case of first onset of proteinuria \geq Grade 2 (i.e., ≥ 1 g in 24 hours by quantitative assessments)	Lucitanib treatment should be withheld and proteinuria monitored by dipstick twice weekly. Upon recovery of proteinuria to Grade ≤ 1 (1+ by dipstick or urinary protein < 1.0 g/24 hours), lucitanib treatment should be resumed at the same dose and dipstick monitoring should continue
In case of second onset of proteinuria \geq Grade 2	Withhold the drug and perform a quantitative assessment of 24-hour urinary protein. Upon recovery, the lucitanib treatment should be resumed with a 2.5 mg dose reduction (e.g., 10 mg to 7.5 mg)
In case of third onset of proteinuria \geq Grade 2	Repeat assessments and dose modifications as outlined above (e.g., 7.5 mg to 5 mg)
In case of fourth onset of proteinuria \geq Grade 2	If proteinuria \geq Grade 2 recurs following dose reductions to 5 mg, or if there is no recovery within 30 days, discontinue treatment permanently

In case of Grade 3 proteinuria or of additional risk factors (e.g., microhematuria, arterial hypertension), assessment of free/conjugated bilirubin, haptoglobin N, schistocytes, and/or renal biopsy may be indicated in consultation with a nephrologist.

Proteinuria will be graded as follows (CTCAE Version 4.0):

Grade 1: 1+ proteinuria; urinary protein < 1.0 g/24 hours

Grade 2: 2+ proteinuria; urinary protein ≥ 1.0 –3.4 g/24 hours

Grade 3: Urinary protein ≥ 3.5 g/24 hours

7.4.3 *Sub-clinical hypothyroidism*

Plasma TSH and thyroid hormones levels should be measured, per protocol. Treatment with levothyroxine 50 µg/day is recommended for patients with TSH values above 5 mIU/L, even if triiodothyronine (T3) and thyroxine (T4) are normal. The treatment with lucitanib can continue at the same dose.

7.4.4 *Decrease in LVEF*

LVEF will be assessed by ECHO or MUGA. It is recommended to use the same technique for a given patient throughout the whole study duration. In case of HF symptoms or modification on imaging from baseline the following rules must be applied:

- No signs of HF and LVEF $\geq 45\%$ OR absolute drop from baseline $\leq 15\%$ EF % points. Continue lucitanib at the same dose level and repeat LVEF assessment per protocol
- Patient is symptomatic OR LVEF $< 45\%$ OR absolute drop from baseline $> 15\%$ EF % points. Hold lucitanib until resolution (LVEF $\geq 50\%$ and asymptomatic). If resolution occurs within 3 weeks, lucitanib can be resumed at a reduced dose by 2.5 mg increments, as described above, otherwise withdraw lucitanib permanently
- No recovery OR LVEF $< 20\%$. Discontinue lucitanib permanently and follow-up the patient

7.4.5 *QT_C prolongation*

In case of CTCAE Grade 3 prolongation of the QT_CF (Fridericia correction) interval > 500 msec, lucitanib treatment must be withheld.

Serum calcium, phosphorus, potassium, and magnesium levels should be analyzed, and levels should be corrected to within normal limits if needed. In all cases a second ECG must be carried out to confirm the QT_CF prolongation > 500 msec within 1 hour of the initial ECG. A review of concomitant medications that could cause QT prolongation and/or Torsades de Points should be performed (see [Section 8](#) and [Appendix C](#)).

Once QT_CF prolongation has resolved, lucitanib may be restarted at a 2.5 mg lower dose. Further dose reductions are permitted, as described above.

Grade 4 QT_C prolongation (QT_C > 501 msec or > 60 msec change from baseline and Torsades de Pointes or polymorphic ventricular tachycardia or symptoms of serious arrhythmia) should result in permanent discontinuation of lucitanib.

7.4.6 *Liver function test abnormalities*

In case of Grade 3 increase in ALT and AST, the dose will be withheld until recovery to Grade 2. If recovery occurs within 14 days, treatment will be resumed at the same dose level. If no recovery occurs within 14 days, the treatment will be resumed at a 2.5 mg lower dose upon recovery. Further dose reductions are permitted, as described above. In case of repeated events at 5 mg or absence of recovery to Grade 2 within 7 days, lucitanib will be stopped permanently.

In case of patient presenting with ALT >3 times the ULN concurrent with a total bilirubin >2 times the ULN with no evidence of hemolysis, and an alkaline phosphatase < 2 times the ULN or not available, lucitanib must be stopped permanently.

Abnormal values in AST and/or ALT concurrent with abnormal elevations in total bilirubin, in the absence of other causes of liver injury, are considered potential cases of drug-induced liver injury (potential Hy's Law cases) and as such, should always be considered important medical events. Patients who present that combination of laboratory abnormalities should be evaluated further to definitively determine the etiology of the abnormal laboratory values.

The patient should return to the investigational site and be evaluated as soon as possible, preferably within 48 hours from awareness of the abnormal results. This evaluation should include laboratory tests, detailed history, physical assessment, and the possibility of hepatic neoplasia (metastases) should be considered. In addition to repeating AST and ALT, laboratory tests should include albumin, total bilirubin, direct bilirubin, prothrombin time (PT) and alkaline phosphatase. A detailed history, including relevant information, such as review of ethanol, recreational drug and supplement consumption, family history, sexual history, travel history, history of contact with a jaundiced subject, surgery, blood transfusion, history of liver or allergic disease, and work exposure, should be collected. Further testing for acute hepatitis A, B, or C infection and liver imaging (e.g., biliary tract) may be warranted. All cases confirmed on repeat testing as meeting the criteria mentioned above with no other cause for liver function test (LFT) abnormalities identified at the time should be considered potential Hy's Law cases irrespective of availability of all the results of the investigations performed to determine etiology of the abnormal LFTs.

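### As written, the LVEF rule puts a patient with no heart failure who fails one criterion under both continue and hold, and the liver rule sets a 7-day permanent stop against 14-day and later resumption

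*Protocol*

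**What the plan says.** **LVEF (Protocol 7.4.4, repeated in the Synopsis).** The rules are mandatory: "In case of HF symptoms or modification on imaging from baseline the following rules must be applied".

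- The continue row opens "No signs of HF and LVEF" and sets a floor of 45%. It then adds, joined by OR, a fall from baseline of no more than 15 points. Its action is "Continue lucitanib at the same dose level and repeat LVEF assessment per protocol".
- The hold row opens "Patient is symptomatic OR LVEF" and sets a value below 45%. It then adds, also joined by OR, a fall of more than 15 points. Its action is "Hold lucitanib until resolution", where resolution means LVEF of at least 50% and no symptoms.

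**Liver (Protocol 7.4.6, repeated in the Synopsis).** A Grade 3 rise in ALT and AST leads to a hold until recovery to Grade 2. Three sentences then govern what follows:

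- Early recovery: "If recovery occurs within 14 days, treatment will be resumed at the same dose level".
- Recovery after that point restarts the drug, once it comes, with the dose cut by 2.5 mg.
- Permanent stop: "In case of repeated events at 5 mg or absence of recovery to Grade 2 within 7 days, lucitanib will be stopped permanently".

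Neither the protocol nor the SAP says which instruction prevails when two apply. The SAP only refers back to the protocol's toxicity criteria.

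**The concern.** A dose-modification rule should send each finding to one action. Here two mandatory rules appear to send some findings to two opposite actions. For LVEF, the hold row is triggered by failing either criterion, while the continue row is satisfied by passing either one. A patient who passes one and fails the other is therefore in both. For the liver, the stop is set at 7 days, inside the 14 days during which same-dose resumption is promised.

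What is at stake is consistent safety dosing for cardiac and hepatic findings. Two sites could act differently on the same result and each cite the protocol. A monitor checking adherence under 13.4 could not say which site departed from it.

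**Working it through.** No figure in the plan is to be reproduced. The check is to list the possible findings and see which instructions each one meets.

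**LVEF**

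Inputs: the 45% and 15-point limits from 7.4.4, and entry LVEF of at least 50% from 6.2, so both examples below can occur.

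The continue row mixes *and* with OR, so it can be grouped in two ways:

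- G1: no signs AND (LVEF ≥45% OR fall ≤15)
- G2: (no signs AND LVEF ≥45%) OR fall ≤15

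For a patient with no signs or symptoms of heart failure:

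| LVEF ≥45% | Fall ≤15 | Example | Continue (G1 / G2) | Hold |
|---|---|---|---|---|
| yes | yes | – | yes / yes | no |
| no | yes | 55 to 43, fall 55 − 43 = 12 | yes / yes | yes (43 < 45) |
| yes | no | 65 to 48, fall 65 − 48 = 17 | yes / yes | yes (17 > 15) |
| no | no | – | no / no | yes |

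Two of the four combinations meet both rows under either grouping.

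The two rows also use different heart failure terms: signs in one, symptoms in the other. Crossing signs, symptoms, LVEF <45% and fall >15 gives 16 combinations:

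| Version of the rule | In both rows | In neither row |
|---|---|---|
| As written, G1 | 5 | 1 |
| As written, G2 | 8 | 0 |
| OR changed to AND, terms left unmatched | 1 | 1 |
| OR changed to AND, *signs or symptoms* in both rows | 0 | 0 |

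**Liver, first Grade 3 event**

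Inputs: the 7-day and 14-day limits from 7.4.6.

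| Recovery to Grade 2 | Above 5 mg, literal | At 5 mg, literal | Above 5 mg, if the 7-day clause is for 5 mg only | At 5 mg, same reading |
|---|---|---|---|---|
| by day 7 | resume same | resume same | resume same | resume same |
| days 8–14 | resume same + stop | resume same + stop | resume same | resume same + stop |
| day 15 on | resume lower + stop | resume lower + stop | resume lower | resume lower + stop |

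Read literally, 4 of 6 cells conflict, and the lower-dose branch can never be reached without the stop having already applied. On the narrower reading, 2 of 6 conflict, both at 5 mg.

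A first liver event at 5 mg is possible. Table 1 takes a 10 mg patient down twice for hypertension: 10 − 2.5 − 2.5 = 5 mg. After day 14 that patient would also be directed to 5 − 2.5 = 2.5 mg, although 7.4.8 treats 5 mg/day as the last allowed reduction step.

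Changing 7 to 14 in the stop sentence and nothing else leaves day 15 onward in conflict at both dose levels.

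These are counts of logical cases, not of patients. The documents give no rate for LVEF decline or for Grade 3 ALT/AST.

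**The case against.** The strongest reply is that a competent site would not be misled.

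- **The protective action is always open.** Section 12.1 requires discontinuation for any event that the investigator judges an unacceptable safety risk, and lists investigator decision as a ground in its own right. Section 7.4.6 also has an unambiguous permanent stop for raised ALT with raised bilirubin, without hemolysis or a raised alkaline phosphatase. This stands. It limits the harm to inconsistency between sites.
- **The LVEF slip is obvious.** With AND in place of OR, the two rows nearly mirror each other, so the intent is easy to guess. That supports a cheap correction, but the mandatory text still says otherwise in two places.
- **The 7-day clause may belong to 5 mg only.** Table 3 on proteinuria pairs recurrence at 5 mg with a recovery limit in a similar way, so this reading is plausible. In 7.4.6, however, the 5 mg condition attaches to repeated events and not clearly to the recovery limit. Even if the reading is granted, the conflict at 5 mg remains.
- **Section 7.4.8 has a limit of more than 14 days' interruption.** It is written for other toxicities and matches neither liver rule.

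A reader might infer more than the documents support:

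- That every Grade 3 liver event recovering after day 7 is in conflict. This holds only on the literal reading.
- That LVEF below 20% is a further contradiction because it meets both hold and discontinue. It is not: the discontinue row reads as an escalation of the hold row, and permanent discontinuation includes holding.
- That the efficacy results or their precision are affected. Nothing in either document shows this.

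**Conclusion.** Both rules are wrong as written.

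- **LVEF:** the conflict holds under either grouping of the continue row. It concerns patients with no signs or symptoms of heart failure who fail exactly one criterion.
- **Liver:** the conflict covers days 8–14 and day 15 onward at every dose if the text is read literally. If the 7-day clause is confined to 5 mg, it covers only a first event at 5 mg recovering after day 7. The text does not settle which reading is meant.

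The effect is inconsistent safety dosing between sites in an unquantified subset. No patient count is claimed, and no effect on PFS, sample size or analysis. Confidence in the two overlaps is high because they follow from the wording alone. The choice of liver rule is a clinical matter for the sponsor.

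**What to change.** **LVEF (7.4.4 and Synopsis).** Make the continue row require all three conditions: no signs or symptoms of HF AND LVEF ≥45% AND a fall from baseline of ≤15 points. Use *signs or symptoms of HF* in the hold trigger and in the resolution criterion as well. If only the trigger is changed, a patient held for signs alone with LVEF of at least 50% would meet resolution at once.

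**Liver (7.4.6 and Synopsis).** The sponsor chooses one complete rule.

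- **Option A, split by dose.** Above 5 mg, recovery to Grade 2 within 14 days resumes the same dose. Later recovery resumes 2.5 mg lower, never below 5 mg, with a stated maximum hold. At 5 mg, a first event recovering within 7 days resumes at 5 mg. No recovery within 7 days, or a repeated event, is a permanent stop.
- **Option B, one limit.** At all doses, recovery within 14 days resumes the same dose. No recovery within 14 days, or a repeated event at 5 mg, is a permanent stop. The lower-dose resumption sentence is deleted, and the sentence allowing further reductions is reworded to match.

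Under either option each of the six liver cells carries one action. Option A must state the 5 mg resumption explicitly, because confining the existing 14-day sentences to higher doses would leave early recovery at 5 mg with no resume dose.

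**Cost.** Text edits in two sections and the Synopsis, by amendment or clarification letter, plus one clinical decision. No added procedures, visits or data.

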7.4.7 Management of Posterior Reversible Encephalopathy Syndrome (PRES)

If a patient presents with symptoms suggestive of PRES (e.g., persisting headache not responsive to usual analgesics, confusion, visual symptoms, seizures and coma), immediately interrupt lucitanib treatment and consider performing all relevant clinical and radiological examinations (e.g., neurological consultation, MRI) in order to ensure early diagnosis and treatment of this syndrome. A follow-up MRI should be performed in order to confirm the diagnosis of PRES, and if confirmed, lucitanib treatment must be permanently discontinued.

7.4.8 Other toxicities

For other Grade 3 or 4 hematologic and non-hematologic toxicities (except for alopecia), lucitanib treatment should be withheld until recovery to Grade 2 for hematological or Grade 1 for non-hematological toxicity. Upon recovery, the drug may be resumed at a 2.5 mg lower dose. Once the dose has been reduced within a treatment cycle, treatment continues at that dose level; no dose escalation is possible within a cycle. If a patient continues to experience toxicity after all allowed dose reduction steps as described above (i.e., after a patient has been dose-reduced from starting dose to 5 mg/day), or if dosing with lucitanib is interrupted for >14 consecutive days due to toxicity, treatment should be permanently discontinued, unless otherwise agreed between the investigator and the sponsor.

In the event of Grade 3 or 4 nausea and vomiting, antiemetics should be used. If, despite maximal antiemetic use, Grade 3 or 4 nausea or vomiting persists, lucitanib treatment should be withheld until recovery and dose reduction and discontinuation should follow the same paradigm as recommended for other Grade 3 and 4 non-hematologic toxicities.

7.4.9 Planned Surgery

In the case of planned surgeries, lucitanib should be temporarily withheld at least 7 days prior to and 7 days after a minor surgery (e.g., line placement, exploratory laparoscopy). Lucitanib should be temporarily withheld at least 14 days prior to and 14 days after a major surgery (e.g., bowel resection, cardiac bypass).

In all cases, lucitanib treatment should not be resumed until the surgical wound is fully healed.

7.5 Accountability of Protocol-Specified Treatment

Study personnel will maintain accurate records of lucitanib shipments/receipts, administration, and drug reconciliation. The study site is responsible for the return or destruction of lucitanib as required. With the exception of lucitanib bottles issued for the PK sub study, a drug management system (IWRS) will manage lucitanib inventory at all sites. Bottles of lucitanib for the PK sub study may be managed locally. For management of all other lucitanib requests and shipments, the IWRS is required. Any lucitanib accidentally or deliberately destroyed must be accounted for. All bottles must be accounted for prior to their destruction at the study center. Unused bottles should be destroyed locally. If destruction at the site is not possible, supply should be returned to the drug depot. During the course of the study and at completion of the study, the number of bottles of lucitanib shipped, destroyed, and returned must be reconciled.

7.6 Blinding/Masking of Treatment

This is an open-label study; the investigational product will not be blinded or masked. All patients enrolled will receive lucitanib.

7.7 Treatment Compliance

Documentation of dosing will be recorded in a study specific diary provided by the sponsor (or designee). Study site personnel will review the dosing information with the patient (or legally authorized representative) on scheduled clinic visit days. Patients (or legally authorized representative) will be asked to record dosing information for lucitanib taken at home in the diary and to bring the diary and all unused lucitanib supplies with them to scheduled clinic visits. A compliance check and lucitanib count will be performed by study personnel. Study site personnel will record compliance information in the eCRF and retain the diary in the patient's medical record.

Lucitanib will be permanently discontinued for patients that fail to take 14 or more doses due to non-compliance (not related to toxicity or planned surgery) within any two consecutive cycles, unless otherwise agreed between the investigator and the sponsor.

8 PRIOR AND CONCOMITANT THERAPIES

8.1.1 Permitted Concomitant Medication and Medications that Should be Used with Caution

All concomitant medications will be recorded in the eCRF. The following concomitant medications are permitted during the study or should be used with caution:

- Lucitanib is highly bound to plasma proteins; therefore, use caution with warfarin, which is also highly bound to plasma protein and has a narrow therapeutic window
- Supportive care (e.g., antiemetics, analgesics for pain control) may be used at the investigator's discretion and in accordance with institutional procedures
- Drugs with possible risk to cause prolonged QT interval and/or possible risk or conditional risk to cause Torsades de Pointes must be used with caution (see [Appendix C](#))
- Transfusion of blood and blood products
- Treatment with antibiotics, anti-emetics, anti-diarrheals, analgesics, thyroid replacement therapy
- Bisphosphonates and denosumab in patients with bone metastases and for which the treatment was initiated prior to the initiation of study drug Considering the risk of drug-drug interactions, concomitant use of moderate inhibitors of CYP2C8 or CYP3A4 are not recommended during the study (see [Appendix E](#))
- Any other medication as appropriate, except for prohibited medications as described in [Section 8.1.2](#) below

8.1.2 Prohibited Concomitant Medications

The following concomitant medications are not permitted during the study:

- Systemic anticancer therapy (e.g., hormonal therapy, immune therapy, targeted therapy), except for bisphosphonates and denosumab in patients with bone metastases
- Prior treatment with bevacizumab within 3 months prior to the first dose of lucitanib
- Radiotherapy during the treatment period is prohibited. Palliative bone radiotherapy at focal sites can be allowed during the screening period, before lucitanib intake and providing recovery is achieved before study drug initiation
- Drugs known to cause prolonged QT interval and/or know risk of causing Torsades de Pointes (see [Appendix C](#))
- Strong inhibitors of CYP2C8 or CYP3A4 are contraindicated during the study. Should acute treatment with a strong inhibitor be deemed necessary, lucitanib must be temporarily withheld. Lucitanib may be resumed after a minimum of seven days of ending acute treatment with a strong inhibitor of CYP2C8 or CYP3A4

- Co-administration of strong inducers of CYP3A4 ([Appendix E](#)) are not permitted at any time during treatment with lucitanib

9 STUDY PROCEDURES

[Table 4](#) summarizes the procedures and assessments to be performed for patients in Cohorts A, B and C with exception of patients in the PK sub study; [Table 5](#) summarizes the procedures and assessments to be performed for patients in the PK sub study.

Unless specified, all procedures and assessments are to be completed within ± 2 days of the scheduled time point and are synchronized with administration day of lucitanib.

Table 4: Schedule of Assessments (All Cohorts)

		Treatment Period (Daily Dosing) ^A						
		Cycle 1			Cycle 2 and Beyond	Cycle 2 Only		
Procedure ^B	Screening	Day 1 ^C	Day 4	Day 15	Day 1	Day 15	End-of-Study	Two Monthly Follow-Up
Informed Consent	X							
Medical/Oncology History	X							
Brief History			X	X		X		
Complete Physical Examination	X	X		X	X		X	
ECOG Performance Status	X	X			X		X	
Vital Signs, Height, Weight ^D	X	X	X	X	X	X	X	
Prior/Concomitant Medications and Procedures	X	X			X		X	
Contraceptive Counseling ^E	X						X	
Serum Pregnancy Test ^F	X						X	
Hematology, Including Reticulocytes ^G	X	X		X	X		X	
Serum Chemistry ^H	X	X		X	X		X	
Urinalysis ^I	X	X	X	X	X	X	X	
Tumor Scans (Including brain imaging for patients with known CNS metastases or when clinically indicated) ^J	X				X		X	
Submit FFPE Tumor Tissue ^K	X						X	
Adverse Events ^L	X	X	X	X	X	X	X	
Lucitanib Dispensation/Administration		X			X			
ECG Assessments ^M	X	X			X		X	
LVEF (ECHO or MUGA) ^N	X				X		X	
Plasma for ctDNA Analysis ^O	X	X		X	X		X	
Plasma PD Biomarker Sampling ^P	X	X		X	X		X	

		Treatment Period (Daily Dosing) ^A						
		Cycle 1			Cycle 2 and Beyond	Cycle 2 Only		
Procedure ^B	Screening	Day 1 ^C	Day 4	Day 15	Day 1	Day 15	End-of-Study	Two Monthly Follow-Up
Blood for Sparse PK Sampling ^Q				X	X			
Pharmacogenomic Blood Sampling		X						
Quality of Life Questionnaire ^R		X			X		X	
Review and Collection of BP and Dosing Diary		X	X		X		X	
Survival Status							X	X
Subsequent Therapies for Breast Cancer							X	X

^A Lucitanib will be administered daily, at least 2 hours before and 2 hours after a meal (on an empty stomach) with water (240 mL or 8 ounces). The total fasting period is 4 hours.

^B Unless specified, procedure is completed ±2 days of scheduled time point. Procedures for C1D4 must be completed ±1 day of scheduled time point.

^C Procedures required prior to lucitanib administration on C1D1 may be omitted if completed ≤3 days earlier during the screening period.

^D Vital signs (BP, pulse, and temperature) taken pre-dose on drug administration days; height is only required once at screening. BP self-monitoring, two times per week, is requested from patients (see [Section 9.5.1.3](#)).

^E Patients are to continue using effective contraception for 6 months after the last dose of lucitanib and report any pregnancies during this period.

^F Serum β-hCG (evaluated by local labs) will be performed only on women of childbearing potential ≤7 days prior to C1D1 and End-of-Study. If the serum pregnancy test results are not available on Day 1, a urine pregnancy test can be performed on Day 1 to confirm that the patient is not pregnant prior to dosing.

^G Includes hemoglobin, hematocrit, WBC and differential (with ANC), platelet count, PT/PTT, and reticulocyte count ≤14 days prior to the first day of dosing. Blood will be sent for analysis at a local laboratory and must be reviewed by the investigator prior to start of lucitanib administration. Additional tests may be performed at the investigator's discretion.

^H Includes TSH, T3, T4, total protein, albumin, creatinine, BUN or urea, total bilirubin, alkaline phosphatase, ALT, AST, glucose, sodium, potassium, chloride, CO₂, calcium, magnesium, and phosphorus, ≤28 days prior to first day of dosing. Total cholesterol will be completed during screening only. Blood will be sent for analysis at a local laboratory and must be reviewed by the investigator prior to start of lucitanib administration.

^I Includes dipstick for protein, glucose, blood, pH, and ketones. If dipstick findings are abnormal, then a microscopic evaluation will be performed to assess the abnormal findings.

^J Tumor scans obtained within 28 days prior to C1D1, may be used as the baseline scans. Scans should preferably be CT scans of the chest, abdomen, and pelvis with intravenous contrast and appropriate slice thickness per RECIST Version 1.1, using the same methods throughout the study that were used to detect lesions at baseline. Other alternative studies (MRI, X-ray) may be performed if clinically indicated. Brain imaging is required at baseline and must be repeated at follow-up tumor assessments for patients with brain lesions. The first on-treatment scan should be completed on C2D1, and every 8 ± 1 weeks through Cycle 6 (i.e., C4D1, C6D1). Thereafter, scans should be completed every 12 ± 1 weeks (i.e., C9D1, C12D1, C15D1, etc.) until disease progression. Tumor scans do not need to be repeated at End-of-Study if <2 weeks since last scan or the patient had disease progression at the last scan. Scans will be evaluated locally for patient treatment decisions. Scans will be sent to a central radiological laboratory.

^K For patient selection, *FGFR1* and 11q amplification status may be determined based on local assessment, or based on central assessment as confirmed by a prescreening process. FFPE tumor tissue is required for all enrolled patients. The post-treatment biopsy is optional and requires additional consent. Detailed sample handling instructions are provided in the Laboratory Manual.

^L AEs will be assessed from the time of first dose of lucitanib through 28 days after the last dose.

^M ECGs will be taken in triplicate anytime during screening, pre-dose (5–10 mins prior to dosing), and approximately 2 hrs (± 5 mins) post-dose on Day 1 of each Cycle, and at End-of-Study, any time after treatment is discontinued.

^N LVEF will be assessed by ECHO or MUGA. It is recommended to use the same technique for a given patient throughout the study. ECHO should be performed at Screening, on C2D1, and every 8 weeks thereafter, and at the End-of-Study.

^O Whole blood will be collected pre-dose and processed locally for plasma ctDNA. Collections occur at screening, C1D1, C1D15, Day 1 of all subsequent Cycles, and End-of-Study. Refer to the Laboratory Manual for sample handling instructions.

^P Whole blood will be collected pre-dose and processed locally for plasma for PD biomarkers. Refer to the Laboratory Manual for sample handling instructions.

^Q Plasma levels for sparse PK of lucitanib will be measured on pre-dose samples collected on C1D15 and Day 1 of Cycles 2, 3, and 5. An additional sample will be collected on C2D1, 1–3 hours post-dose.

^R Quality of Life Questionnaire (FACT-B) should be collected from the patient prior to dosing at C1D1; then on Day 1 of Cycles 3, 5, and 7. After Cycle 7, questionnaires will be collected every 3 cycles (on Day 1 Cycles 10, 13, 16, etc.) and at End-of-Study.

Table 5: Schedule of Assessments (PK Sub Study)

Procedure ^B	Screening	Day -7	Treatment Period (Daily Dosing) ^A					End-of-Study	Two Monthly Follow-Up
			Cycle 1			Cycle 2 and Beyond	Cycle 2 Only		
	Day -28 to Day -8		Day 1 ^C	Day 4	Day 15	Day 1	Day 15		
Informed Consent	X								
Medical/Oncology History	X								
Brief History				X	X		X		
Complete Physical Examination	X	X	X		X	X		X	
ECOG Performance Status	X	X	X			X		X	
Vital Signs, Height, Weight ^D	X	X	X	X	X	X	X	X	
Prior/Concomitant Medications and Procedures	X	X	X			X		X	
Contraceptive Counseling ^E	X							X	
Serum Pregnancy Test ^F	X							X	
Hematology, Including Reticulocytes ^G	X	X	X		X	X		X	
Serum Chemistry ^H	X	X	X		X	X		X	
Urinalysis ^I	X	X	X	X	X	X	X	X	
Tumor Scans (Including brain imaging for patients with known CNS metastases or when clinically indicated) ^J	X					X		X	
Submit FFPE Tumor Tissue ^K	X							X	
Adverse Events ^L	X	X	X	X	X	X	X	X	
Single Dose Lucitanib Tablet Administration ^M		X							
Lucitanib Dispensation/Administration ^M			X			X			
ECG Assessments ^N	X	X	X			X		X	

	Screening		Treatment Period (Daily Dosing) ^A						
			Cycle 1			Cycle 2 and Beyond	Cycle 2 Only		
Procedure ^B	Day -28 to Day -8	Day -7	Day 1 ^C	Day 4	Day 15	Day 1	Day 15	End-of-Study	Two Monthly Follow-Up
LVEF (ECHO or MUGA) ^O	X					X		X	
Plasma for ctDNA Analysis ^P	X		X		X	X		X	
Plasma PD Biomarker Sampling ^Q	X		X		X	X		X	
Blood for Sparse PK Sampling ^R					X	X			
Pharmacogenomic Blood Sampling			X						
Quality of Life Questionnaire ^S			X			X		X	
Review and Collection of BP and Dosing Diary		X	X	X		X		X	
Survival Status								X	X
Subsequent Therapies for Breast Cancer								X	X
Intensive PK Sampling ^T		X	X						

^A Lucitanib will be administered daily, at least 2 hours before and 2 hours after a meal (on an empty stomach) with water (240 mL or 8 ounces). The total fasting period is 4 hours.

^B Unless specified, procedure is completed ± 2 days of scheduled time point. Procedures for C1D4 must be completed ± 1 day of scheduled time point.

^C Procedures required prior to lucitanib administration on C1D1 may be omitted if completed ≤ 3 days earlier during the screening period. The total time from the Day -7 visit to the Cycle 1 Day 1 visit must not be fewer than 7 days, but may be greater than 7 days, if necessary.

^D Vital signs (BP, pulse, and temperature) taken pre-dose on drug administration days and post-dose following collection of the 24 hr PK samples on Day -7 and Day 1; height is only required once at screening. BP self-monitoring, two times per week, is requested from patients, including between Day -7 and Day 1 (see [Section 9.5.1.3](#)).

^E Patients are to continue using effective contraception for 6 months after the last dose of lucitanib and report any pregnancies during this period.

^F Serum β -hCG (evaluated by local labs) will be performed only on women of childbearing potential ≤ 7 days prior to C1D1 and End-of-Study. If the serum pregnancy test results are not available on Day 1, a urine pregnancy test can be performed on Day 1 to confirm that the patient is not pregnant prior to dosing.

^G Includes hemoglobin, hematocrit, WBC and differential (with ANC), platelet count, PT/PTT, and reticulocyte count ≤ 14 days prior to the first day of dosing. Blood will be sent for analysis at a local laboratory and must be reviewed by the investigator prior to start of lucitanib administration. Additional tests may be performed at the investigator's discretion.

^H Includes TSH, T3, T4, total protein, albumin, creatinine, BUN or urea, total bilirubin, alkaline phosphatase, ALT, AST, glucose, sodium, magnesium, potassium, chloride, CO₂, calcium, and phosphorus ≤ 21 days prior to first day of dosing. Total cholesterol will be completed during screening only. Blood will be sent for analysis at a local laboratory and must be reviewed by the investigator prior to start of lucitanib administration.

^I Includes dipstick for protein, glucose, blood, pH, and ketones. If dipstick findings are abnormal, then a microscopic evaluation will be performed to assess the abnormal findings.

^J Tumor scans obtained within 21 days prior to C1D1, may be used as the baseline scans. Scans should preferably be CT scans of the chest, abdomen, and pelvis with intravenous contrast and appropriate slice thickness per RECIST Version 1.1, using the same methods throughout the study that were used to detect lesions at baseline. Other alternative studies (MRI, X-ray) may be performed if clinically indicated. Brain imaging is required at baseline and must be repeated at follow-up tumor assessments for patients with brain lesions. The first on-treatment scan should be completed on C2D1, and every 8 \pm 1 weeks through Cycle 6 (i.e., C4D1, C6D1). Thereafter, scans should be completed every 12 \pm 1 weeks (i.e., C9D1, C12D1, C15D1, etc.) until disease progression. Tumor scans do not need to be repeated at End-of-Study if < 2 weeks since last scan or the patient had disease progression at the last scan. Scans will be evaluated locally for patient treatment decisions. Scans will be sent to a central radiological laboratory.

^K For patient selection, *FGFR1* and 11q amplification status may be determined based on local assessment, or based on central assessment as confirmed by a prescreening process. FFPE tumor tissue is required for all enrolled patients. The post-treatment biopsy is optional and requires additional consent. Detailed sample handling instructions are provided in the Laboratory Manual.

^L AEs will be assessed from the time of first dose of lucitanib through 28 days after the last dose.

^M On Day -7 a dose of the lucitanib tablet formulation will be given followed by a dose of the lucitanib capsule formulation on Day 1.

^N ECGs will be taken in triplicate anytime during screening, pre-dose (5–10 mins prior to dosing), and approximately 2 hr (± 5 min) post-dose on Day -7 (Cohort C) and Day 1 (All Cohorts) of each Cycle, and at End-of-Study, any time after treatment is discontinued.

^O LVEF will be assessed by ECHO or MUGA. It is recommended to use the same technique for a given patient throughout the study. ECHO should be performed at Screening, on C2D1, and every 8 weeks thereafter, and at the End-of-Study.

^P Whole blood will be collected pre-dose and processed locally for plasma ctDNA. Collections occur at screening, C1D1, C1D15, Day 1 of all subsequent Cycles, and End-of-Study. Refer to the Laboratory Manual for sample handling instructions.

^Q Whole blood will be collected pre-dose and processed locally for plasma for PD biomarkers. Refer to the Laboratory Manual for sample handling instructions.

^R Plasma levels for sparse PK of lucitanib will be measured on pre-dose samples collected on C1D15 and Day 1 of Cycles 2, 3, and 5. An additional sample will be collected on C2D1, 1–3 hours post-dose.

^S Quality of Life Questionnaire (FACT-B) should be collected from the patient prior to dosing at C1D1; then on Day 1 of Cycles 3, 5, and 7. After Cycle 7, questionnaires will be collected every 3 cycles (on Day 1 Cycles 10, 13, 16, etc.), and at End-of-Study.

^T PK specimens will be collected at the following time points on Day -7 and Day 1: 5–10 min pre-dose, post-dose at 15 (± 2) min, 30 (± 3) min, 1 hr (± 5 min), 1.5 hr (± 5 min), 2.5 hr (± 10 min), 4 hr (± 15 min), 6 hr (± 15 min), 8 hr (± 15 min), 10 hr (± 30 min) (optional), and 24 hr (± 30 min).

